4.1.19. Handling of Incomplete or Missing Dates

Incomplete or missing start and end dates will be imputed for adverse events to determine treatment-emergence and for medications/non-drug therapies to determine when the medication/non-drug therapy was taken (i.e., pre-dose, concomitant, or post last dose of IMP). Incomplete dates will also be imputed for date of Initial Diagnosis where required.

An incomplete date occurs when the exact date an event occurred or ended cannot be obtained from a participant. The database contains data fields for month, day, and year. A date is incomplete if at least one of these three fields is not known.

For many of the planned analyses, a complete date is necessary to determine if the event should be included in the analysis (e.g., if the event is treatment-emergent) or to establish the duration of an event. In such cases, incomplete dates will be imputed.

For the purposes of handling partially reported start and stop dates for an event the following algorithm will be applied:

- Missing start day, but month and year present:

If the event occurs in the same month and year as the occurrence of IMP, then the start day of the event will be assigned to the day of first dose of IMP (i.e., Day 1).

Otherwise, the start day will be set to the first day of the month.

- Missing start day and month, but year present:

If an event occurs in the same year as IMP, then the start date of the event will be assigned to Day 1.

Otherwise, the start day and month will be set to 01 January.

- In the unlikely event of a completely missing start date (year not present), for adverse events the start date will be imputed as Day 1.

- Missing end day, but month and year present:

The day will be set to the last day of the month.

- Missing end day and month, but year present:

The end day and month will be set to the date of study completion.

However, if the study completion year is greater than the year of the event, then the day and month will be set to 31 December.

- Missing all components of an end date and the event is not marked as ongoing:

The event will be considered as ‘ongoing’ and will be considered treatment-emergent if the start date is on or after Day 1.

If any imputed start date causes the start date to occur after the end date, the end date will be used for the imputation of the start date. If any imputed date causes the end date to occur prior to the start date of the event, the start date of the event will be used for the imputation of the end date. If the imputed date is later than the date of study withdrawal, then the date of study withdrawal will be imputed for the date. In participant data listings, start and stop date of events will be displayed as reported on the eCRF (i.e., imputed values will not be listed).

4.1.20. Handling of Alphanumeric Data

Should there be instances where a clinical laboratory parameter is reported with imbedded non-numeric characters, for example, “<0.1” or “>10”, the data will be imputed for quantitative summaries. The actual values as reported in the database will be presented in data listings.

For incorporation in quantitative summaries (except for concentration data), the following imputation rules will be employed:

- The lower limit of quantification (LLOQ) will be replaced with $\frac{1}{2}$ the value of the lower limit. For example, < 0.1 will be replaced with 0.05.
- The upper limit of quantitation will be increased by one level of precision that precedes the value. For example, >0.1 will be imputed to “0.11”, and >10 will be imputed to “10.1”.
- Additionally, the ULN/lower limit of normal (LLN) values may be reported as alphanumeric (e.g., ‘ <5 ’, ‘ ≤ 5 ’, ‘ >5 ’, ‘ ≥ 5 ’). In these cases, if the ULN or LLN is necessary for determination of the laboratory severity grade, the following conventions will be employed:
 - If the value is in the form of ≤ 5 , the ULN will be populated with the value after removing the symbol (i.e., the ULN is set to 5). If the value is in the form of <5 , the ULN will be decreased by two levels of precision in the direction of the symbol (i.e., the ULN is set to 4.99).
 - If the value is in the form of ≥ 5 , the LLN will be populated with the value after removing the symbol (i.e., the LLN is set to 5). If the value is in the form of >5 , the LLN will be increased by two levels of precision in the direction of the symbol (i.e., the LLN is set to 5.01).

4.2. Analysis Periods

The start and ends dates of each analysis period (following the study design) are used for the classification of efficacy data and will be assigned sequentially according to the study day of the event.

Table 4: Definition of Analysis Periods for Efficacy Data

Analysis Period	Duration	Start Day	End Day
Baseline Period	~2 Weeks	The greater of: Study Day -14 or Informed consent	Study Day, -1
Titration Period	~2 Weeks	Study Day, 1	The lesser of: Day 15 minus 1 or **Early termination (minus 1) or End of Treatment

Analysis Period	Duration	Start Day	End Day
Maintenance Period	~12 Weeks	Day 15	The lesser of: Day 98 (Visit 6) or Early Termination (if > Day 15)

** If a participant experiences early termination from the study and continues to Maintenance Period, end dates will be bound by early termination minus 1, while the start of Maintenance Period will begin on the date of early termination.

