4.1.5. Days on Treatment

Days on study is the number of days from Day 1 to the date of study completion or early termination as recorded on the END OF STUDY CRF.

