4.1.13. Last Two Weeks of Maintenance Treatment

The last two weeks of maintenance treatment for an individual participant is defined as the 14 days leading up to and including the last dose of IMP. For aggregate analysis, the last two weeks of maintenance treatment is defined as two weeks prior to Visit 6 (Week 14). A participant must have a minimum of 14 days of treatment in the maintenance phase to be considered for this metric.

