5.8. Exposure to Treatment

The number of participants who received IMP, number of days on IMP, number of treatment discontinuations, reasons for treatment discontinuation, and treatment compliance will be summarized by treatment group for the FAS: Expanded Analysis Set. Drug accountability data will be listed.

5.9. eDiary Compliance

Primary, secondary, and other efficacy variables are based on diary-collected panic attack frequencies, and as such, diary compliance will be evaluated along with treatment compliance. Participants are instructed to complete their diary entries at least once a day during the study. A diary day will be considered missing for compliance if a panic attack diary record is missing for that day. Diary compliance will be evaluated during the Screening Period, the Baseline Period, the Titration Period, the Maintenance Period, the entire Treatment Period, and the last two weeks of Maintenance Treatment.

eDiary compliance will be calculated as 100 times the number diary days (days with diary completed) during the period and dividing this quantity by the expected number of diary days that should have been completed during this period of time. Compliance is computed for actual time of participation in the study through Visit 8 follow-up. If a participant did not enter an analysis period, the diary compliance for the analysis period will not be calculated.

eDiary compliance data will be listed by treatment then participant for each diary type and summarized by treatment group and version of diary used.

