6. CHANGES IN THE PLANNED ANALYSES

Analysis methods described here reflect revisions to strategic focus and scope and will supersede those described in the protocol. In addition to changes corresponding to protocol amendments, the analysis plan differs from the statistical analysis section of the protocol as described below:

- As a result of early closure of enrollment and early treatment discontinuation of ongoing participants, planned sample size will not be achieved and proportion of participants with treatment discontinuation will be increased. The resulting sample size will have insufficient power for hypothesis tests and thus, efficacy analysis will be exploratory.
 - The following changes were made to the protocol-specified statistical analysis to reflect the strategic shift to an exploratory evaluation of efficacy
 - Multiplicity adjustments were removed
 - Most sensitivity analyses were removed
 - Supportive analyses involving panic attack-related endpoints were added using an expanded FAS population including all participants regardless of eDiary version used
- Description of handling of ICEs was expanded and revised for the primary and key secondary endpoints:
 - Additional detail was provided for different types of ICEs (eg, administration of rescue medication and treatment discontinuation)
 - Composite strategy was replaced with treatment policy and while on treatment strategies for handling ICEs for analysis of primary and key secondary endpoints
- Added description of missing diary data handling:
 - For the primary efficacy outcome (proportion of participants free of panic attacks), outcome for participants who did not report a panic attack and had <12/14 days of completed eDiary was set to missing, unless otherwise indicated
 - For key secondary efficacy outcome (change from baseline in the frequency of panic attacks), outcome for participants with <7/14 days of completed eDiary was set to missing
- The SAP replaced the SAS® procedure GLIMMIX (specified in protocol) with GENMOD to fit binomial repeated measures model to estimate the proportion of participants that were free of panic attack and the treatment difference. Although both procedures can fit binomial repeated measures model, model-fitting is more efficient with the GENMOD procedure.

Should any deviations from the analyses pre-specified in the authorized statistical analysis plan arise, such deviations will be documented in the final clinical study report.

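### SAP Table 4 gives two conflicting start days for the Maintenance Period of participants who terminate early after reaching it

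*SAP*

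**What the plan says.** **Table 4, Maintenance row (SAP 4.2).** The start is Day 15. The end is "The lesser of: Day 98 (Visit 6) or Early Termination (if > Day 15" (closing bracket follows).

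**Table 4, Titration row.** The start is Day 1. The end is the earliest of Day 14 (written as Day 15 minus 1), ET minus 1, or end of treatment. The double asterisk stands on the ET item of this cell; the Maintenance row carries no mark.

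**Footnote to Table 4.** Its condition is "If a participant experiences early termination from the study and continues to Maintenance Period". Its rule is that "end dates will be bound by early termination minus 1, while the start of Maintenance Period will begin on the date of early termination".

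**Where the period is used.** Section 5.9 evaluates eDiary compliance separately for Titration, Maintenance and other periods, and adds: "If a participant did not enter an analysis period, the diary compliance for the analysis period will not be calculated". Section 4.1.13 ends an individual's last-two-weeks window on the last dose and then requires: "A participant must have a minimum of 14 days of treatment in the maintenance phase to be considered for this metric". It neither defines the maintenance phase nor cites Table 4.

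**Other definitions.** Table 3 sets the two-week Maintenance intervals through Week 10 by fixed study days, beginning with Days 15-28. Section 4.1.5 is headed Days on Treatment, but its text begins "Days on study is the number of days from Day 1 to the date of study completion or early termination", the same text as 4.1.4. Section 4.1.8 defines Days on IMP, which ends at the last dose.

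**Who is affected.** Section 6 refers to "early treatment discontinuation of ongoing participants" and expects a higher proportion of treatment discontinuations. It gives no number.

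**The concern.** The Maintenance row and the footnote give different start days for the same participant: someone who passed Day 15 and then left early. Such a person has terminated early and has continued to Maintenance, so both parts of the footnote's condition appear to be met. Two programmers working from the same table could derive different periods.

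If the footnote is followed, nearly all target-dose days of these participants drop out of the Maintenance Period without being assigned to any other. The direct casualty is diary compliance for that period. There may also be an indirect one. The 14-day minimum in 4.1.13 decides who has a last-two-weeks value, and that window defines the primary endpoint. If the minimum is checked against the Table 4 period, the footnote would remove participants who had ample time at target dose. The sponsor closed the study and stopped ongoing participants, so early termination is the situation in which the period rules need to be clear.

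**Working it through.** **Inputs.** From Table 4: Maintenance start Day 15, planned end Day 98, the ET end rule, the Titration end rule and the footnote. From 4.1.13: the 14-day minimum. From 4.1.18: Visit 6 on Day 98 and Visit 9 on Day 131. Length of a period = end − start + 1.

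**1. The plan's own figure.** Planned Maintenance: 98 − 15 + 1 = 84 days; 84 / 7 = 12.0 weeks. This agrees with the stated duration of about 12 weeks.

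**2. Length after early termination under each rule.**

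- (a) Row: ET − 15 + 1.
- (b) Footnote start with the row's end: ET − ET + 1 = 1.
- (c) Footnote start with an end at ET minus 1: (ET − 1) − ET + 1 = 0, so the end precedes the start.
- Days 15 to ET − 1 left unassigned under (b) or (c), with Titration ending on Day 14: ET − 15.

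| ET day | (a) Row | (b) | (c) | Days 15 to ET − 1 in no period under (b) or (c) |
|---|---|---|---|---|
| 16 | 2 | 1 | 0 | 1 |
| 20 | 6 | 1 | 0 | 5 |
| 28 | 14 | 1 | 0 | 13 |
| 42 | 28 | 1 | 0 | 27 |
| 60 | 46 | 1 | 0 | 45 |
| 70 | 56 | 1 | 0 | 55 |
| 90 | 76 | 1 | 0 | 75 |

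Under (c) the ET day itself is also unassigned.

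**3. eDiary compliance.** Section 5.9 takes 100 × completed diary days / expected diary days. For ET on Day 60 the denominator is 46 under (a). Under (b) it is 1, so compliance can only be 0% or 100%. Under (c) it is 0, so compliance is undefined, or is dropped as if the participant had never entered the period.

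**4. The 14-day minimum.** Under (a), ET − 15 + 1 ≥ 14 requires ET ≥ 28. Under (b) and (c) the length is 1 or 0 for every ET day, so the minimum is never met. This step takes the last dose to fall on the ET date and the maintenance phase in 4.1.13 to be the Table 4 period.

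**5. Can the footnote be confined to the cell that carries it?** For ET on Day 60 the Titration end is min(14, 59) = Day 14. The marked item is not selected, and the footnote has nothing to do. For ET on Day 10 the Titration end is min(14, 9) = Day 9, and the footnote would open Maintenance on Day 10. That is before the Day 15 start, contrary to the row's own condition "Early Termination (if > Day 15" and contrary to the fixed 14-day titration with no dose modification permitted (Protocol 6.5). The footnote's condition in any case excludes someone who does not continue to Maintenance. Confined in this way, it is empty or conflicts with the row. The minus 1 still leaves Day 10 in no period.

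**6. Section 4.1.5.** For a completer the text runs to Day 131, against Day 98 for Days on IMP, a difference of 131 − 98 = 33 days. Exposure (5.8) summarises days on IMP and disposition (5.6) summarises days on study. No analysis section uses Days on Treatment.

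**The case against.** The best defence is that the mark sits only on the Titration end-day cell. The Maintenance row is unmarked, and applying the row alone gives 46 days for ET on Day 60. On that view the footnote never takes effect and nothing is distorted. This stands in part: the SAP has not clearly replaced Day 15, and Table 3 also counts Maintenance from Day 15. The defect is therefore an unresolved contradiction. But the footnote names the start of the Maintenance Period outright, and limiting it to its cell gives it no valid use.

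A reader might infer more than the documents support:

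- *That the primary endpoint window itself is wrong.* Section 4.1.13 anchors the window on the last dose and Table 3 on the end of treatment. Neither uses the footnote. Any effect runs through the 14-day minimum alone.
- *That a participant who stops during titration acquires a one-day Maintenance Period.* The footnote covers only someone who continues to Maintenance.
- *That the split of adverse events by titration or maintenance onset (5.17.1) is affected.* Section 4.2 limits Table 4 to efficacy data, and 5.17.1 does not cite it.
- *That 4.1.5 lets off-drug days count towards the 14-day minimum.* Section 4.1.13 does not cite 4.1.5 and speaks of treatment within maintenance. The copy error affects completers too, so it is not specific to early stoppers.
- *That a large or calculable share of participants is affected.* The documents give neither a count nor a distribution of stopping days.

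It is also fair that section 6 declares the efficacy analysis exploratory and underpowered, which limits the consequence.

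**Conclusion.** The contradiction is real and should be reconciled. For a participant who terminates early after reaching Maintenance, the row gives ET − 15 + 1 maintenance days and the footnote, read literally, gives 1 or 0. For ET on Day 60 that is 46 against 1 or 0, with Days 15 to 59 unassigned.

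Two consequences follow if the footnote is applied. Maintenance-Period eDiary compliance is distorted; this rests only on the literal reading. Failure of the 14-day minimum by participants with ET on Day 28 or later needs a further assumption, that the maintenance phase in 4.1.13 is the Table 4 period, and the SAP does not say so. How many participants are concerned cannot be derived from the documents.

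Section 4.1.5 is a separate, minor copy error without effect on maintenance time.

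**What to change.** 1. In Table 4, delete the double-asterisk footnote and the minus 1 on early termination in the Titration row. Titration then ends at the earliest of Day 14, ET or end of treatment.
2. State that Maintenance runs from Day 15 to the end day already in Table 4, only for participants still on treatment at Day 15.
3. In 4.1.13, state that the 14 days are counted from Day 15 to the last dose.
4. As a minor correction, delete 4.1.5 or align it with Days on IMP in 4.1.8.

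The cost is SAP wording and a few lines of derivation code, with no new data and no change in trial conduct. If the SAP can no longer be amended, the rule applied can be recorded in the clinical study report, where section 6 already provides for documenting deviations.

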Study Day of Early Termination or Unscheduled Visit	Analysis Visit	Analysis Visit Target Day
< 1 Predose	Baseline	1
≥ 1 to 28	Day 14 (Visit 3)	14
> 28 to 56	Day 42 (Visit 4)	42
> 56 to 84	Day 70 (Visit 5)	70
> 84 to 100	Day 98 (Visit 6)	98
> 100	Day 131 Follow-up (Visit 9)	131

Table 12: Visit Windows for Safety Laboratory Urine Sample Assessments

Study Day of Early Termination or Unscheduled Visit	Analysis Visit	Analysis Visit Target Day
< 1	Baseline	1
≥ 1	Day 98 (Visit 6)	98

Table 13: Visit Windows for PK Sampling

Study Day of Early Termination or Unscheduled Visit	Analysis Visit	Analysis Visit Target Day
1 to 21	Day 14 (Visit 3)	14
22 to 49	Day 42 (Visit 4)	42
50 to 77	Day 70 (Visit 5)	70
>77	Day 98 (Visit 6)	98

5. STATISTICAL ANALYSIS METHODS

5.1. GENERAL CONSIDERATIONS

Descriptive statistical methods will be used to summarize the data from this trial, with statistical testing performed for the efficacy endpoints. Unless stated otherwise, the term “descriptive statistics” refers to number of participants (N), number of observations (n), arithmetic mean, median, standard deviation (SD), coefficient of variation (CV%) (for concentration data only), first quartile (Q1), third quartile (Q3), minimum, and maximum for continuous data, and frequencies and percentages for categorical data. Certain figure presentations will include the standard error of the mean (SE). The term “treatment group” refers to treatment assignment: 25 mg darigabat and placebo. All data collected from participants who sign the informed consent form, including screen failures, will be included in data listings. Unless otherwise noted, the data listings will be sorted first by treatment group and participant number and then by date within each participant number.

The statistical analyses will be conducted with the SAS® software package version 9.4 or higher.

5.2. Analysis Sets

The analysis sets are defined as follows:

Table 14: Analysis Set Descriptions

Term	Description	Analysis
All Screened Participants	All Screened Participants includes all participants who signed the informed consent form.	Disposition
Intent-to-Treat Analysis Set (ITT)	All randomized participants.	Demographic and Baseline Characteristics
Safety Analysis Set	All randomized participants who receive at least 1 dose of IMP.	Safety analysis
Full Analysis Set (FAS)	
FAS: Panic Attack Endpoints
 
All randomized participants who receive at least 1 dose of IMP and have valid baseline panic attack assessments and have recorded all baseline/post-baseline panic attack assessments in an eDiary that requires collection of reports contemporaneous to the day being assessed and collection of the presence/absence of each associated symptom (i.e. eDiary Version 2). Participants who have not met all inclusion/exclusion criteria but are randomized in error will not be included.
	All efficacy analysis (including primary) related to panic attack events captured by eDiary

Term	Description	Analysis
	FAS: Expanded All randomized participants who receive at least 1 dose of IMP and have valid baseline panic attack assessments. Participants who have not met all inclusion/exclusion criteria but are randomized in error will not be included.	Sensitivity efficacy analysis (including primary) related to panic attack events as specified
PK Analysis Set	All randomized participants who receive at least 1 dose of IMP and have at least 1 measurable darigabat concentration.	PK analysis

Abbreviations: FAS=full analysis set; IMP=investigational medicinal product; ITT=intent-to-treat; PK=pharmacokinetic.

5.3. Statistical Hypotheses

The hypotheses of interest for the efficacy endpoints are 2-sided tests of superiority comparing the darigabat (DAR) with placebo.

$$H_0: \mu_{\text{placebo}} = \mu_{\text{DAR}} \text{ vs } H_1: \mu_{\text{placebo}} \neq \mu_{\text{DAR}}$$

5.4. Multiplicity Adjustment

No multiplicity adjustments will be made for this Phase 2 study.

5.5. Strata and Covariates

The randomization will be stratified by evidence-based psychotherapy for the treatment of anxiety disorders including panic disorder with 2 strata: receiving evidence-based psychotherapy (initiated >3 months prior to the Screening Visit) or not receiving evidence-based psychotherapy. The baseline value of each efficacy variable will be included as a covariate in the efficacy analyses based off collection in CRF. For analysis of freedom from panic attacks and panic attack frequency, baseline PDSS score will also be included as a covariate.

5.6. Participant Disposition, Demographic and Baseline Characteristics

Participant disposition will be based on all participants randomized with tabulation of the number of participants who completed the study, the number who completed treatment, the number of participants discontinued from the study/treatment, and the reasons by treatment group. Additionally, the number of days on study will be summarized.

Participant disposition data will also be tabulated for all participants screened to include the number of participants screened, the number of screen failures, and the reason for screen failure.

The number of participants in each analysis set will be summarized.

Additionally, the number of participants randomized will be summarized by treatment group and overall.

A listing of randomization number, randomization date, participant, treatment randomized, treatment received, and inclusion in each analysis set will be prepared.

Demographic data and baseline characteristics including age at screening, sex, fertility status, race, ethnicity, height at screening, weight at screening and baseline, body mass index (BMI) at screening and baseline, years since initial diagnosis of panic disorders, baseline panic attack frequency, proportion of participants free of panic attacks at baseline, proportion of participants receiving evidence-based psychotherapy baseline PDSS total score, , baseline CGI-S score, and baseline HAM-A total score will be summarized by treatment using descriptive statistics for the ITT Analysis Set.

